### 9.2 SAMPLE SIZE DETERMINATION

We anticipate randomizing, in an equal allocation ratio, a total of 350 participants with follow-up through at least 6 months, which will be the main time point for primary analysis.

**Aim 1.** For the primary test of comparative effectiveness of cCBT vs. m-Education for the trial, the power calculation is based on the comparison of intervention groups for the main outcome of change in daily pain intensity; the effect size we are powered for also applies to the key secondary outcomes: pain interference and depression (PHQ-9). Specifically, we have 80% power to detect a difference of 0.37 standard deviations between study arms on 6-month changes in the outcome. Additionally, we are accounting for 15% attrition at 6 months.

**Aim 2.** For the tests of interactions, we will identify baseline depressive symptom subgroups with either low or high depression (PHQ  $\leq$  10 versus PHQ  $>$  10). In order to detect small-moderated effect sizes (similar to the main effect in Aim 1) for the HTE, we would need approximately four times as many participants as we do for Aim 1 (N=1400). Median trial size in SCD is 142; less than 50% of trials meet  $>90\%$  of their recruitment target. Thus, achieving the required sample size would not be feasible; however, when combined with our qualitative data, the quantitative data from Aim 2 will be critical for informing future dissemination of the intervention.

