#### 9.4.6 SUB-GROUP ANALYSES

The objective of Aim 2, examining heterogeneity of treatment effect (HTE), is to determine whether the intervention works better for some than for others. We again pre-specify our analysis plan and will examine differences in main outcomes for patients with high ( $\text{PHQ-9} > 10$ ) versus low ( $\text{PHQ-9} \leq 10$ ) depression. These subgroups are most relevant so that end results can meaningfully inform patients about what works best for whom, and in turn, better support individuals as they seek treatment for pain. Furthermore, in examining differential impact of the interventions, based on these subgroups, providers, payers, and other decision makers can target resources in a manner that best meets the needs of those in need of services, reduces variations in practice, and improves health outcomes. We will augment the primary analysis models for pain intensity with relevant main effects for baseline depression level, and 2- and 3-way interactions with study arm and time. Of primary interest will be the significance of the 3-way interaction (time-by-study arm-by-baseline depression level). If significant, we will present treatment effect estimates and measures of variability in the form of confidence intervals within each subgroup. Two-sided tests of level 0.05 of the interactions between intervention and HTE subgroup will allow us to test whether depression moderates impact of intervention on pain outcomes. Although

hypotheses are stated with direction, we will conduct two-sided tests to be conservative. For all of the above described models, we will focus on the 6-month outcome.

---

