We will examine the heterogeneity of the treatment effect to determine whether the intervention works better for some than for others. Our prespecified analysis plan will examine differences in pain interference between patients with high (PHQ-9>10) and low (PHQ-9≤10) depression. We will augment the primary analysis models for pain interference with relevant main effects for the baseline depression level and 2- and 3-way interactions with the study arm and time. Of primary interest is the significance of the 3-way interaction (time×study arm×baseline depression level). If significant, we will present the treatment effect estimates and 95% CIs within each subgroup. For all of the above-described models, we will focus on the 6-month outcome.

Mediation Analysis

For coping skills, self-efficacy, and program engagement or dose measures, changes in scores from baseline to 3 months and from baseline to 6 months will be tested as potential mediating variables. We will use the framework of Kraemer et al to calculate effect sizes, accounting for the impact of the potential mediator variable. In addition to modeling each mediator as a function of time, study arm, time×study arm interaction, study site, and baseline depression level (PHQ-9≤10 vs PHQ-9 >10), we will augment the original primary analytic models by including the potential mediator as a covariate.

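### The only planned Aim 2 moderation test splits baseline PHQ-9 into two groups, which costs roughly a quarter to a half of the moderator information if moderation is roughly linear in the score

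*SAP*

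**What the plan says.** The protocol, section 9.2 (Aim 2), sets the coding: "we will identify baseline depressive symptom subgroups with either low or high depression", cut at 10. Section 9.4.6 builds the test on it: "Of primary interest will be the significance of the 3-way interaction (time-by-study arm-by-baseline depression level"). It sets the error rate as "Two-sided tests of level 0.05 of the interactions between intervention and HTE subgroup". The SAP, under Subgroup Analysis, keeps the same two groups and compares pain interference "between patients with high (PHQ-9>10) and low (PHQ-9≤10) depression". It then states: "Of primary interest is the significance of the 3-way interaction" of time, arm and depression level. The SAP itself gives no alpha for this test.

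Both documents promise estimates within each subgroup only if that interaction is significant. Neither plans a moderation analysis with the score itself.

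Four other statements bear on the point:
- The SAP's description of PHQ-9 gives a total from 0 to 27 with graded severity thresholds at 5, 10, 15 and 20.
- Protocol section 9.2 says an interaction of Aim 1 size would need about 1,400 participants, calls that infeasible, and intends Aim 2 to be read with the qualitative data.
- Protocol section 9.4.6 justifies the subgroups by their use to patients, providers and payers.
- Protocol section 8.2 gives the PHQ-8 to Web respondents who are not affiliated with a participating clinical site.

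**The concern.** The Aim 2 question is about symptoms, and the instrument grades symptoms. The test then treats scores of 0 and 10 as identical and scores of 10 and 11 as different. If the benefit of one arm over the other changes gradually with depression, that coding loses precision in the very aim for which the protocol already concedes that it cannot recruit enough people.

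A second consequence follows from the reporting rule. Subgroup estimates appear only after a significant interaction, so low power also means that the estimates meant for decision makers will usually not be shown. What is at stake is the information Aim 2 yields. The primary comparison of the arms is not affected.

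**Working it through.** **Inputs.** 350 randomised 1:1 (protocol 9.2: "in an equal allocation ratio, a total of 350 participants"). 15% attrition (protocol 9.2 and SAP), so n = 350 × 0.85 = 297.5 evaluable. Two-sided 0.05 (protocol 9.4.6). Interaction size 0.37 SD, taken from the Aim 1 statement ("we have 80% power to detect a difference of 0.37 standard deviations between study arms on 6-month changes in the outcome") because section 9.2 uses an Aim 1-sized effect for Aim 2. The share p with PHQ-9 above 10 is not given. I **assume** 22-57%, the range the protocol background (section 2.2) quotes for clinically important depressive symptoms in SCD. That is neither a PHQ-9 > 10 figure nor specific to this chronic-pain sample. The score distribution and the shape of moderation are also not given.

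**1. The plan's own figure.** The variance of an interaction relative to a main effect is 1/[p(1−p)]. At p = 0.5 this is 4, and 4 × 350 = 1,400, which reproduces the protocol. At p = 0.57 it is 4.08 (1,428); at p = 0.22 it is 5.83 (2,040). The 1,400 inherits the Aim 1 sample size as stated. Whether 350 matches 0.37 SD at 80% power is a separate question and is not used here.

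**2. Power with the split.** SE = 2/√[n·p(1−p)]; power = Φ(0.37/SE − 1.96).

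**3. Information retained by the split (normal score, linear moderation).** This is the squared correlation between the score and its indicator, φ(z_p)²/[p(1−p)]. At p = 0.5: 0.3989²/0.25 = 0.637. At p = 0.22: 0.2961²/0.1716 = 0.511.

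**4. Power with the score.** For the same underlying slope, divide 0.37/SE by √retained.

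| p | SE | 0.37/SE | Power, split | Retained | Loss | Power, score |
|---|---|---|---|---|---|---|
| 0.22 | 0.280 | 1.322 | 26% | 0.511 | 49% | 46% |
| 0.50 | 0.232 | 1.595 | 36% | 0.637 | 36% | 52% |
| 0.57 | 0.234 | 1.580 | 35% | 0.629 | 37% | 51% |

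A 20,000-run simulation agrees: split 25.7%, 35.6% and 35.0%; score 45.0%, 51.0% and 50.5%.

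**5. Bounded scores.** PHQ-9 cannot be normal on 0-27. I took beta-binomial shapes with assumed mean 6-12 and SD 4.5-7, keeping those with 22-57% above 10, and still assumed linear moderation.
- On whole-number means and half-point SDs the loss runs from 24.1% (mean 6, SD 7) to 35.9% (mean 8, SD 4.5). A finer grid moves the upper end to about 37-38%.
- Power is about 26-36% with the split and 34-50% with the score. The gain is 7-15 percentage points within a scenario.

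**6. Step at the cut.** If the effect jumps exactly at the cut, the split loses nothing and the linear test is misspecified. Multiply 0.37/SE by √retained instead. At p = 0.5: 1.595 × 0.798 = 1.273, power 25% against 36%. At p = 0.22: 1.322 × 0.715 = 0.945, power 16% against 26%. The simulation gives 24.3% and 15.6% for the score.

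**7. Reporting rule.** With 26-36% power, the subgroup estimates would be withheld in 64-74% of trials in which a 0.37 SD difference truly exists.

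**The case against.** The split is pre-specified and has a stated purpose. The cut lies next to a recognised severity threshold and was not chosen from the data. The qualitative sample is stratified at the same value (protocol 4.1), and Aim 2 is to be read with those interviews. A two-group test answers a question about high and low depression directly. The documents do not say that moderation is linear, and under a step at the cut the present test is the better one. Replacing it also does not rescue an aim whose required sample size the protocol already calls infeasible.

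Much of this stands. The step case is a real cost of changing the test, so a reader should not infer that the change is free of any trade-off. Nor do the documents support saying outright that more than a third of the information is lost: that figure needs both a normal score and linear moderation, and bounded scores mostly give somewhat less.

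What does not stand is the argument that decision makers' need for subgroups requires a two-group test. Test and display are separable, and showing subgroup results only after significance serves those readers poorly. No passage argues for a step at 10, while the aim is worded in terms of symptoms and the SAP lists graded thresholds.

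**Conclusion.** The point holds in a conditional form, as a cheap improvement and not as a flaw in the primary analysis. If moderation is roughly linear in PHQ, the split discards roughly a quarter to a half of the moderator information: about 24-37% for the assumed bounded scores and 36-49% for a normal score. Power for a 0.37 SD high-low difference is about 26-36% with the split and about 34-52% with the score. These figures rest on an assumed 22-57% above the cut, 15% attrition and a two-sided 0.05 test. If moderation is a step exactly at the cut, the order reverses.

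Two further readings are tempting but not supported. One is that the continuous score would make Aim 2 adequately powered; it stays well under 80% in every scenario examined. The other is that the two-level depression covariate in the primary, secondary and utilisation models should change too. Nothing calculated here bears on those models.

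**What to change.** Amend the SAP's Subgroup Analysis before any unblinded analysis:

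- **Test.** Make time × arm × continuous baseline PHQ, evaluated at 6 months and two-sided at 0.05, the single Aim 2 test.
- **Score.** Use a score that every participant has, such as the eight items shared by PHQ-8 and PHQ-9 (8 × 3 = 24 maximum), because eight- and nine-item totals cannot be pooled without a rule. State how the two display groups are formed for PHQ-8 respondents.
- **Shape.** Name a check for non-linearity, for example a spline, as supportive only, since it spends degrees of freedom that the aim can ill afford.
- **Display.** Show the fitted treatment effect across the score with 95% CI. Report the estimates in both depression groups with 95% CI whether or not the interaction is significant. This keeps the link to the interview strata and partly covers the step scenario.

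The cost is SAP wording and a scoring rule; no new data, visits or enrolment are needed. The downside to record is the lower power of the linear test if the effect really is a step at the cut.

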Cognitive Behavioral Therapy and Real-Time Pain Management Intervention for Sickle Cell Via Mobile Applications (CaRISMA)

NCT04419168

1/13/2023

Statistical Analysis Plan

Study Design & Objectives. CaRISMA is a multisite, randomized, pragmatic, comparative effectiveness trial that will be conducted at 6 comprehensive sickle cell centers and 4 community-based organizations (CBOs). A total of 350 adults with SCD who report chronic pain and/or use long acting or daily opioids will be enrolled and randomized in a 1:1 ratio to receive either a digital CBT program tailored for adults with SCD (CBT) or pain and SCD education (Education) on their mobile phones for 12 weeks. Both programs will use identical mobile-based technology platforms, with the only difference being the content provided. The focus of the digital CBT program is to teach behavioral coping skills through participants' seeing and doing, whereas the pain education arm focuses on improving self-management through participants' learning and knowing more about pain and SCD.

The primary objective of the CaRISMA (Cognitive Behavioral Therapy and Real-time Pain Management Intervention for Sickle Cell via Mobile Applications) trial is to compare the effectiveness of two mobile phone-delivered programs for reducing SCD pain symptoms at the 6-month follow-up: digital CBT versus pain and SCD education (Education). We will also evaluate the sustainability of the intervention effects at the 12-month follow-up. The secondary objective is to assess whether baseline depression symptoms moderate the effect of interventions on pain outcomes. We hypothesize that digital CBT will confer greater improvement in pain interference, pain intensity, and depressive symptoms at 6 months compared with Education. We also hypothesize that digital CBT will confer a greater reduction in health care use (e.g., opioid prescriptions or refills or acute care visits) over 12 months compared with Education.

Randomization. Upon completion of eligibility, participants will be randomly assigned to either digital CBT or Education. Permuted block randomization will be stratified by study center (e.g., one of the six clinical sites or from a community partner) in an effort to control for site-specific disease education and treatment approaches. The randomization schema was created by the lead statistician in the data coordinating center and integrated into the web-based data capture system.

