Sample Size Calculation. For the primary test of comparative effectiveness of digital CBT versus mobile education (m-Education) for the trial, the power calculation is based on the comparison of intervention groups for the main outcome of the 6-month change in pain interference. Specifically, our sample size of 350 participants enables 80% power to detect a difference of 0.37 SDs between study arms on 6-month changes. This detectable effect is also applicable to key secondary outcomes, such as pain intensity and depression, as measured by the PHQ-9. Our calculations account for 15% attrition at 6 months.

Hypotheses. Our study hypotheses are:

H1: cCBT will confer greater benefit on pain outcomes at 6 months, compared to m-Education. The primary outcome of the proposed trial is change in pain interference at 6 months. The main secondary outcome will be change in average weekly pain intensity. We will also explore sustainability of the intervention effects at 12 months.

H2: cCBT will confer greater benefit on depressive symptoms at 6 months, compared to m-Education.

H3: cCBT will confer greater decreases in health care utilization (opioid prescriptions, acute care visits) and opioid misuse behaviors (Current Opioid Misuse Measure – COMM) over 12 months, compared to m-Education.

Analysis Sets. All analyses will be under the framework of intention-to-treat, such that all randomized participants are included regardless of initiation or adherence to interventions. However, we will conduct sensitivity analyses restricting to participants who were randomized with confirmation of sickle cell disease.

Study Outcomes.

Primary Pain Outcome: Pain Interference

Patient Reported Outcomes Measurement Information System Pain Interference assesses the effect of patient-reported pain on relevant aspects of a person's life and may include the extent to which pain hinders engagement with social, cognitive, emotional, physical, and recreational activities. This measure will only be completed at baseline and 3, 6, and 12 months.

Secondary Pain Outcome: Daily Pain Intensity

Participants will be asked to enter their daily pain via a mobile website. They will receive reminder notifications via text messages for 2-week periods at baseline and 3, 6, and 12 months. However, between these automated-reminder periods, participants will be encouraged to continue entering their pain scores on the mobile pain web app.

Other Secondary Outcomes

Painimation

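### Subgroup effects by baseline depression appear only if an underpowered interaction test is significant: at 0.37 SD they would probably be withheld, and if shown they would exaggerate the subgroup difference

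*SAP*

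**What the plan says.** The SAP (Subgroup Analysis) adds the two- and three-way interactions of baseline depression (PHQ-9 above 10 versus 10 or below) with arm and time to the pain interference model, with the focus on 6 months. It names the deciding test, "Of primary interest is the significance of the 3-way interaction (time×study arm×baseline depression level", and then sets the reporting rule: "If significant, we will present the treatment effect estimates and 95% CIs within each subgroup".

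Protocol section 9.4.6 has the same rule for the pain intensity model: "If significant, we will present treatment effect estimates and measures of variability in the form of confidence intervals within each subgroup". It also fixes the test: "Two-sided tests of level 0.05 of the interactions between intervention and HTE subgroup". The SAP states no level.

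Protocol section 9.2 (Aim 2) says that an interaction of about the Aim 1 size would need roughly 1400 participants, and concludes: "Thus, achieving the required sample size would not be feasible". It then says that the quantitative Aim 2 results, read together with the interviews, are essential for later dissemination. The SAP does not repeat the caveat about power.

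Neither document plans to show the subgroup effects when the interaction is not significant.

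**The concern.** The plan concedes that the test has too little power, and then lets that test decide whether the subgroup estimates are seen. Two things follow. When the test is not significant, a reader gets no effect size or interval by depression level, and a non-significant result at low power cannot separate no moderation from moderation as large as the planned main effect. When the test is significant, the estimates shown have been selected for being far apart, so they exaggerate the difference. Aim 2 asks which programme works for whom, and that question needs the estimates and their uncertainty in either case.

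**Working it through.** **1. The protocol's own figure.** With 1:1 allocation, SD = 1 and share p in the high-depression subgroup, the variance of the treatment effect is 4/N and that of the interaction is 4/(N p(1−p)). The ratio is 1/(p(1−p)), which is 4 at p = 0.5, and 4 × 350 = 1400. The figure reproduces for equal subgroups. At p = 0.22 the ratio is 1/0.1716 = 5.83, or about 2040 participants.

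The Aim 1 statement behind it, "our sample size of 350 participants enables 80% power to detect a difference of 0.37 SDs between study arms on 6-month changes", does not reproduce. With 297.5 evaluable the standard error is 2/√297.5 = 0.116, so power at 0.37 SD is Φ(0.37/0.116 − 1.96) = 89%. This does not rescue Aim 2. Taking the stated 80% at face value gives a main-effect standard error of 0.37/2.80 = 0.132. The interaction standard error at 50:50 is then 0.264, and power is Φ(0.37/0.264 − 1.96) = 29%, which is lower than the value found below.

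**2. Inputs.**
- Evaluable N: 350 × 0.85 = 297.5 (SAP, Sample Size Calculation: "Our calculations account for 15% attrition at 6 months").
- Allocation: "randomized in a 1:1 ratio" (SAP, Study Design & Objectives), taken to hold within each subgroup.
- Test: two-sided 0.05 (protocol 9.4.6).
- True interaction: 0.37 SD, the size that protocol 9.2 has in mind when it refers to the Aim 1 effect.
- Share with PHQ-9 above 10: **assumed**. The protocol background gives 22% to 57% for clinically significant depressive symptoms in sickle cell disease, and its definition may differ from PHQ-9 above 10. I add 30% and 50% as intermediate values.

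**3. Power and selection at a true 0.37 SD.** SE = √(4/(297.5 p(1−p))). Power = Φ(0.37/SE − 1.96) + Φ(−0.37/SE − 1.96). The smallest significant estimate is 1.96 × SE. The last column is the mean absolute estimate given significance, divided by 0.37.

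| Share high | SE | Power | Withheld | Smallest significant | Mean shown / true |
|---|---|---|---|---|---|
| 22% | 0.280 | 26.2% | 73.8% | 0.549 | 1.94 |
| 30% | 0.253 | 31.0% | 69.0% | 0.496 | 1.78 |
| 50% | 0.232 | 35.8% | 64.2% | 0.455 | 1.65 |
| 57% | 0.234 | 35.2% | 64.8% | 0.459 | 1.67 |

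Any estimate that passes must exceed 0.45 to 0.55 SD, which is already above the true 0.37. With no attrition (N = 350), power is still only 30% to 41%. A joint 3-df test over all follow-up times, assuming a correlation of 0.5 between changes, gives about 24% to 34%.

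**4. Other true interactions (split 22% to 57%).**

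| True interaction | Power | Withheld |
|---|---|---|
| 0 | 5% | 95% |
| 0.20 SD | 11–14% | 86–89% |
| 0.37 SD | 26–36% | 64–74% |
| 0.50 SD | 43–58% | 42–57% |
| 0.74 SD | 75–89% | 11–25% |

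**5. What happens to the subgroup effects themselves.** Take true effects of 0.37 SD (high depression) and 0 (low). At 50:50 the mean interaction shown is 1.65 × 0.37 = 0.61, an excess of 0.24. The excess divides between the subgroups in proportion to their variances, here equally, so the mean effects shown are 0.37 + 0.12 = 0.49 and 0 − 0.12 = −0.12. At 22:78 they are 0.64 and −0.08. One subgroup is overstated and the other understated. Coverage of the nominal 95% intervals, given display, is about 90% to 93%. With no true interaction it is about 44% to 83%.

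**6. Reporting without the condition.** The estimates are not selected and coverage is nominal. Half-widths of the 95% intervals are ±0.32 SD in each subgroup at 50:50, and ±0.49 (high) and ±0.26 (low) at 22:78. For the interaction they are ±0.45 to ±0.55 SD. Power does not change.

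**The case against.** Requiring an interaction test before interpreting subgroups is sound practice and guards against over-reading chance differences. That stands as a rule for claiming moderation. It is not a reason to withhold the estimates, and the fix keeps the test.

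A reader might infer that Aim 2 will report nothing in most cases. The documents do not support that. The interaction test is itself the prespecified Aim 2 result and is not conditional on anything. The qualitative comparison by arm and PHQ level (protocol sections 4.1 and 9.4.3) is also independent of it. What is lost is the within-subgroup estimates and their intervals, which interviews cannot supply.

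A reader might also infer that every subgroup effect shown would be inflated. Step 5 shows otherwise: the factor of 1.65 to 1.94 belongs to the between-subgroup difference, and the weaker subgroup is biased downwards.

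Two further points have some force. Withholding is less likely for large interactions. And protocol sections 2.3.3 and 6.2.1 foresee possible sharing of de-identified data and release of a codebook and code, so the estimates might be recovered later. That is a possibility, not a planned report.

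**Conclusion.** The reporting rule should be changed. It makes the usable quantitative output of Aim 2 depend on a test that the protocol says it cannot power. At a true interaction of 0.37 SD, with 297.5 evaluable and an assumed 22% to 57% in the high-depression subgroup, the subgroup estimates would be withheld about 64% to 74% of the time. When shown, the subgroup difference would be exaggerated about 1.65- to 1.94-fold. It would be going too far to say that they are withheld in most cases whatever the truth: at 0.50 SD it is near even, and at 0.74 SD they would usually be shown.

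The figures rest on a normal approximation on the scale of the SD of 6-month change and on an assumed subgroup split. The existence of the rule rests on neither. The primary comparison, the participants and the data collection are unaffected.

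**What to change.** - In the SAP (Subgroup Analysis) and protocol section 9.4.6, delete the opening condition that ties presentation to significance.
- Always report the 6-month treatment effect with its 95% confidence interval in each depression subgroup, and the interaction estimate with its 95% confidence interval, all labelled exploratory.
- Keep the interaction test as the only basis for a claim of moderation, and state its level (two-sided 0.05) in the SAP.
- Specify this for pain interference, the SAP's primary outcome, and align protocol section 9.4.6, which names pain intensity. Otherwise the same edit would leave two different tables specified.
- Carry the protocol's caveat about low power into the SAP. The intervals will show the precision actually achieved.

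The cost is a few sentences across the two documents and one extra table from a model that is already planned. The downside is some risk that readers over-interpret imprecise subgroup estimates; the exploratory label and the wide interaction interval limit it.
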